5. STUDY PROCEDURES

5.1 Intervention arm: Healers assigned to the intervention arm (N=10) will attend a half-day training session prior to trial initiation, led by District HIV clinic staff. This training session will demonstrate proper use and disposal of the point-of-care HIV testing kit and provide training regarding patient pre- and post-test counseling. Healers will be instructed to discuss the benefits of linking to HIV care, including importance of initiating treatment for HIV infection, reducing possible transmission to others, and health benefits of starting ART early, as part of post-test counseling. In addition, this training session will discuss resources available at the ISS clinic, including mental health counselors, family and partner support groups, counselors trained to discuss serostatus disclosure strategies, and reproductive health counselors. Supplies for point-of-care HIV testing and biohazard-compliant disposal will be provided to healers at the start of the trial. HIV 1/2 antibody point of care test (Oraquick[©]) will be administered to participants who agree to test. This test is non-invasive, conducted using oral fluids (rather than whole blood), and is FDA-approved for adult use, with results in 20 minutes. Test results are clearly marked with lines, rather than letters or numbers; this test is validated for use by non-medical personnel, with 99.9% specificity and 91.6% sensitivity. Clients with positive tests will be referred to the HIV clinic for Western Blot confirmation, and linkage to care. Following the healer visit, participants will be contacted once per month, for a period of 3 months, to assess for POC test results, and linkage to care for those who test HIV+.

5.2 Control arm: Control arm healers (N=10) will participate in a half-day session prior to trial initiation, led by District HIV clinic staff. This educational session will discuss WHO and Ministry of Health guidelines for HIV testing, who should receive HIV testing and how often, and where to receive it. Participating patients of healers will then receive “enhanced standard of care” as part of the control arm of the trial. Following the visit, study staff will contact the client once per month, for 3 months, to assess for HIV testing since enrollment in the study.

5.3 Follow up: We will contact participants using their mobile phone numbers. If unable to reach after multiple attempts, study staff will call the backup contact to inquire about the participant’s (taking care not to mention HIV). If this inquiry is not informative, study staff will visit the participant’s home, wearing unmarked clothes and not speaking about HIV with anyone except privately with the participant. In 2014, a Pew Research Center survey indicated that 65% of Ugandans owned a mobile phone (<http://www.pewglobal.org/2015/04/15/cell-phones-in-africa-communication-lifeline/>); therefore, we anticipate that a majority of participants will have a mobile contact number. If unable to reach the participant at their mobile phone number after multiple attempts, the backup contact will be called. If no mobile number is available for the participant, we will ask for a mobile number for a backup contact to use for communication. Study staff will call the backup contact to attempt to speak with the participant (taking care not to mention HIV). All calls will be made from study cell phones, not linked to any hospital or clinic, such that caller ID or callbacks to the outgoing number will not indicate correlation with HIV research. This process will be followed for participants in both the intervention and control groups. If these inquiries via phone are not informative, a single member of the study staff will visit the participant’s home at the address provided, via personal vehicle, wearing unmarked clothes. This staff member will ask to speak with the participant, and will not discuss the study, or the topic of HIV with anyone, except privately with the participant. If home visits are necessary to establish follow-up, we will send a gender-matched staff member (i.e., female staff member for female participant), to minimize suspicion from family or partners who may not be aware of client’s participation in the study. This staff member will describe him/herself as a friend from Mbarara, who is inquiring about the whereabouts of the participant.

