This novel approach will have significant public health impact by expanding HIV testing and linkage to care, thereby reducing morbidity, mortality, and HIV transmission in a highly endemic region. This approach could be scaled for delivery in other HIV-endemic, medically pluralistic communities. Pilot results will be integrated with data from ongoing research in southwestern Uganda to propose a large-scale, cluster-randomized trial of this community-based HIV testing program in Eastern Africa.

Study Duration: 12 months (July 2019 – June 2020)

Primary Endpoint: Rate of HIV testing among TH clients at 3 months

Secondary Endpoints: i) number of new HIV diagnoses among TH clients at 3 months post enrollment; ii) percentage of patients with +HIV POC test who successfully link to HIV care at 3 months post enrollment and iii) variables that predict HIV testing.

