4. RECRUITMENT AND ENROLLMENT

4.1 Inclusion and Exclusion Criteria: Inclusion criteria for healer clients are 1) 18 year of age or older; 2) able to provide informed consent, 3) not known to be HIV infected; 4) willing to be contacted for monthly follow up for 3 months; and 5) willing to complete an exit survey after 3 months. For the intervention (HIV testing) arm, participants must agree to receive their POC HIV test results. Exclusion criteria include being under the age of 18, incapable of giving informed consent, previously being diagnosed with HIV, being unwilling to receive HIV test results, and

unwilling to participate in the testing intervention. Participating healers are eligible to participate if they meet the UNAIDS definition of traditional healer⁸, and are willing to participate in study procedures. We will select from among healers with patient volume greater than 7 patients per week in order to ensure that participant recruitment progresses in a timely manner for this pilot study.

4.2 Informed Consent: We will obtain written informed consent from both traditional healers (N=20) and their clients (N=500) participating in this study. Participating clients must consent to providing three telephone contact numbers (self, friend, and family member), home address, and permission for the research team access to medical records from the District HIV clinic. In addition, they must consent to a home visit, if they are not reachable for follow up via phone. Healers must consent to keeping a logbook of which patients received HIV testing (intervention arm) or referred to HIV testing (control arm).

4.3 Subject Enrollment: One research assistant will be assigned to each arm of the study and will base themselves at healer practices to consecutively enroll 25 clients from each healer until we reach a sample size of N=500 (four-month enrollment period). The research assistant will assign a unique study ID number to each participant, collect demographic information, and locator information for the participant and two back up contacts. This information will be used for monthly follow-up assessments, and to deliver the exit interview.

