6. STATISTICAL CONSIDERATIONS

6.1 Outcomes: The primary outcome for this Aim is *rate of HIV testing among TH clients*. Secondary outcomes will include i) *new HIV diagnoses among TH clients*, ii) *patients with +HIV test who successfully link to HIV care in 3 months*³⁰, and iii) variables that predict HIV testing. The results of this Aim are central to demonstrating feasibility for a subsequent R01 proposal.

6.2 Analysis plan: Descriptive statistics will characterize participants and summarize the data. A multi-level logistic regression model – with individual clients in level 1 nested within healers in level 2 – will be used to calculate the odds ratio for primary outcomes within three months in the intervention compared with the control arms. Adjusted analyses will be conducted as secondary or sensitivity analyses using multivariable, multi-level analyses for both binary and continuous variables. All analyses will be performed in R software.

6.3 Intervention evaluation: 3 months following enrollment, all participants will be contacted for an exit survey to understand experiences of participation in the study, undergoing HIV testing, or deciding not to test. In-depth interviews will be conducted with participating healers at the close of the intervention to obtain feedback on delivering POC testing at their practice locations and assess how the study may have impacted their beliefs and practices.

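### Client contact is the only written way to establish linkage to HIV care; linkage is undefined, and the clinic records every client must release have no stated role

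*Combined protocol and SAP*

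**What the plan says.** The Protocol Summary lists as a secondary endpoint the "percentage of patients with +HIV POC test who successfully link to HIV care at 3 months post enrollment". Section 6.1 repeats it as patients with a positive test "who successfully link to HIV care in 3 months". Neither place defines a successful link or names a data source.

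The procedure is in Section 5.1: "participants will be contacted once per month, for a period of 3 months, to assess for POC test results, and linkage to care for those" with a positive result. Section 5.3 gives the mode: "We will contact participants using their mobile phone numbers", then the backup contact, then a home visit. Section 5.1 also says: "Clients with positive tests will be referred to the HIV clinic for Western Blot confirmation, and linkage to care". Control-arm follow-up (Section 5.2) is only "to assess for HIV testing since enrollment in the study".

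Section 4.2 requires each client to give "permission for the research team access to medical records from the District HIV clinic".

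**The concern.** If the plan is followed as written, the study learns who linked by asking the client. Three things make that answer fragile.

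- Healers are told to discuss the benefits of linking to care as part of post-test counseling, and the same study later asks whether it happened. Some clients who did not go may say that they did.
- Section 8.1.2 describes stigma, rejection and partner violence after a diagnosis, and Section 5.3 allows for partners who do not know of the client's participation. Some clients who did go may deny it.
- Positive clients are sent to the clinic for both confirmation and linkage. Without a definition, a client who attended only for the confirmatory test could be counted either way.

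A client who cannot be reached has no contact-based linkage status at all. The consented clinic records could help with each of these problems, but the plan gives them no role. Linkage is the pilot's evidence that a positive test at a healer's practice leads to care, so an unverified percentage would be a weak basis for planning the larger trial.

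**Working it through.** **1. Where linkage could be ascertained.** Reading the sections side by side:

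| Section | Content | Clinic records used for linkage? |
|---|---|---|
| 3.1 healer logs | test given, or referral made | no |
| 4.2 consent | access to District HIV clinic records required | purpose not stated |
| 5.1, 5.3 follow-up | monthly contact by phone or home visit | no |
| 6.1 outcomes | linkage in 3 months | source not named |
| 6.2 analysis | model for primary outcomes; descriptive statistics | no |
| 6.3 exit survey | experiences, testing decisions | no |
| 7.5 quality assurance | consent forms, eligibility checklists, data files | no |

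Client contact is the only written route.

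**2. Size of the denominator.** Inputs: 250 clients, 90% uptake and 9% prevalence (Section 4.4); sensitivity 91.6% and specificity 99.9% (Section 5.1).

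- The plan's own figure: 250 × 0.90 × 0.09 = 20.25, which reproduces.
- True positives on the test: 20.25 × 0.916 = 18.5.
- False positives: 225 × 0.91 × 0.001 = 0.2.
- Expected positives: 18.5 + 0.2, about 19. One client is 1/18.8 = 5.3 points.
- With the 74% testing rate given for the intervention arm in the Summary of Changes: 185 × 0.09 × 0.916 + 185 × 0.91 × 0.001 = 15.3 + 0.2 = 15.4 positives, or 6.5 points per client.

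**3. Effect of misreporting.** The documents give no linkage or misreporting rate, so every rate here is an assumption. Let p be true linkage, s the share of linked clients who say so, and m the share of unlinked clients who say they linked. Reported linkage = p·s + (1 − p)·m.

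| True p | Over-report only (s = 1, m = 10–30%) | Under-report only (s = 90–70%, m = 0) | Both (s = 95%, m = 10%) |
|---|---|---|---|
| 40% | 46–58% | 36–28% | 44% |
| 60% | 64–72% | 54–42% | 61% |
| 80% | 82–86% | 72–56% | 78% |

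The last column lies above the truth at 40% and 60% and below it at 80%. The net direction therefore depends on rates that are not known.

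**4. Error of records alone.** If a share e of linked clients attends a clinic outside the permission, recorded linkage = p·(1 − e). At p = 60% and e = 10–30% this is 54–42%, a shift of −6 to −18 points, against +4 to +12 for over-reporting at the same assumed rates. Neither source is safe alone.

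**5. Sampling error.** The exact 95% interval for 11 of 19 is 34–80%. Misclassification comes on top of this, and the interval does not reflect it.

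**The case against.** The strongest reply is that the plan never says self-report decides the endpoint. Record access is compulsory, the text offers no other purpose for it, and a record check may well be intended. Section 8.3 says consent forms are attached for each aim; these forms and the figure in Section 3.1 were not available to this review and could state the purpose. This stands. A reader might infer that the sponsor has chosen reported over actual linkage, but the documents show only that client contact is the sole written method.

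A reader might also infer that the percentage must be inflated. The stigma described in Section 8.1.2 gives a reason for denial too, so an upward-only bias is not supported.

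Third, the records are not a complete answer. They cover one clinic, and the plan speaks of the District HIV clinic (Section 4.2), the ISS clinic (Section 5.1) and the Mbarara Referral Hospital HIV clinic (Section 8.1.4) without saying whether they are the same. Counting any clinic visit as linkage would also still include attendance for confirmation only. Both points stand, and they shape the fix.

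Finally, the endpoint is a descriptive percentage of about 19 people in a pilot that Section 4.4 calls exploratory, and its sampling interval is wider than most of the shifts shown. Section 6.1 calls the results of the whole Aim central to the next proposal, not linkage alone. That limits the importance of the point. It does not remove it, because the remedy is so small.

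**Conclusion.** The point holds as a gap in ascertainment. Linkage has no definition, its only written source is the client's account, and a second source that is already consented has no assigned role. Each misclassified client moves the percentage by about 5 points on about 19 positives. At an assumed true linkage of 60%, misreporting of 10–30% in one direction gives a reported figure between 42% and 72%. The 19 rests on the plan's uptake, prevalence and test accuracy; the misreporting rates are assumptions, and the direction of error is open.

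The scope is limited. Only intervention-arm clients receive the study's point-of-care test, and no linkage assessment is written for controls, so this is effectively a one-arm secondary figure. The between-arm comparison of testing, the sample size and the power are unaffected. It is a worthwhile, inexpensive improvement and not a flaw that endangers the trial.

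**What to change.** Amend Sections 5.1 and 6.1 as follows.

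1. Define linkage as a recorded entry into HIV care within 3 months of enrollment, distinct from attendance for confirmatory testing only. The investigators should name the record entry that counts.
2. Confirm that the Section 4.2 permission covers the clinic to which positive clients are referred, and use one clinic name throughout.
3. Check every client with a positive point-of-care test against those records, including clients not reached at follow-up.
4. Use the monthly contact to identify care received elsewhere, and classify it as reported-only.
5. Report two percentages on the same denominator: record-confirmed linkage, and record-confirmed plus reported-only linkage. If the records are correct and clients who attended elsewhere say so, true linkage lies between the two.

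The cost is a few sentences of protocol text and about 20 record look-ups. The downside is that the record-confirmed figure misses care at other clinics and may understate linkage, which is why both figures should be shown.

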3. STUDY DESIGN

3.1 Design: Previously conducted qualitative work and observational data will inform implementation of a pilot study, offering HIV testing at traditional healer locations in southwestern Uganda. No compensation will be provided for healers in the intervention or control arms of the intervention. We will follow Ugandan National protocols²⁹ to administer voluntary HIV counseling and testing at healer practices in Mbarara District. Clustering for this trial will occur at the level of healer practices. For the intervention arm, we will recruit 250 clients

from ten healer practice locations. For the control arm, we will observe 250 healer clients at ten healer locations undergoing “enhanced standard of care”, where healers will participate in a pre-trial educational session describing community HIV resources available for clients, and how to access them. Enrollment will take place from twenty traditional healer practices, over a period of four months. The follow up period will be three months. Primary outcome for this intervention *will be rates of HIV testing among TH clients (Figure).*

[figure not shown]

Figure. Approach for HIV testing pilot

select half to participate in the intervention arm (N=10); the remaining half will participate in the control arm (N=10). Healers in both study arms will keep a log of participants indicating whether HIV testing was delivered (intervention) or if the participant was referred to HIV testing (control). Many healers have little formal education and describe themselves as “illiterate”; study logbooks will be created accordingly. Research assistants will create stickers with de-identified study identification numbers for each participant. The healer will place the participant ID sticker in the log book (thereby avoiding the need to be able to write numbers); logs will show pictures for receiving point-of-care HIV testing, or not testing (in the intervention arm), or referral to the District HIV clinic for HIV testing, or not referring (for the control group). Healers will circle the corresponding picture for each participant based on the outcome of the session. Research assistants will be on site, or reachable via mobile phone, to answer any questions the healers have about record keeping or study procedures.

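### Monthly contacts are described with different HIV-testing content in each arm, and no source covering both arms is assigned to the single 3-month testing rate

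*Combined protocol and SAP*

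**What the plan says.** The Protocol Summary gives the primary endpoint as "Rate of HIV testing among TH clients at 3 months". Section 6.1 repeats it without a time point, and 6.2 compares it between arms as an odds ratio from a multi-level logistic model. None of these places limits the endpoint to POC tests or names a data source.

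The sources described elsewhere are:

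- **Monthly contacts, intervention arm (5.1):** made "to assess for POC test results, and linkage to care for those who test HIV" positive.
- **Monthly contacts, control arm (5.2):** "study staff will contact the client once per month, for 3 months, to assess for HIV testing since enrollment in the study".
- **Healer logs (3.1):** kept in both arms, "indicating whether HIV testing was delivered (intervention) or if the participant was referred to HIV testing (control").
- **Exit survey (6.3):** given to all participants at 3 months. Its stated purpose is to understand experiences of taking part, of testing or of choosing not to test.
- **District HIV clinic records (4.2):** all clients consent to access. No outcome is tied to them.

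On whether every intervention client is tested, 4.1 requires that "participants must agree to receive their POC HIV test results" and excludes people "unwilling to participate in the testing intervention". Yet 5.1 says the test "will be administered to participants who agree to test", the intervention log in 3.1 has a picture for not testing, and 4.4 expects 90% uptake.

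**The concern.** A rate compared between arms should count the same events, found in the same way, in each arm. Here the control contacts ask about any test, while the intervention contacts list only the POC result and linkage. The logs do not close the gap, because a referral is not a test and the control log records only referrals.

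The clients affected are intervention clients who had no POC test at the healer's practice and were tested somewhere else within 3 months. Nothing in 5.1 prompts staff to ask them about it. A control client with the same history is asked.

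What is at stake is the meaning and size of each arm's rate more than whether an effect is detected. That still matters, because the pilot's rates are meant to support a proposal for a larger cluster-randomized trial.

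**Working it through.** **1. The plan's own figure.** The Summary of Changes assumes 39% against 74%, an intracluster correlation of 0.2, 30 clients per cluster, 80% power and alpha 0.05 (taken as two-sided).

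- A two-proportion calculation with pooled variance and no continuity correction gives 31 per arm.
- Design effect: 1 + (30 − 1) × 0.2 = 6.8.
- 31 × 6.8 = 210.8 per arm; 210.8 / 30 = 7.03, rounded up to 8 clusters per arm.
- This is 16 clusters and 480 clients, as stated.

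The planned difference is 74 − 39 = 35 points. With 10 clusters of 25 per arm, the design effect is 1 + 24 × 0.2 = 5.8 and normal-approximation power is about 92%.

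**2. Tests elsewhere that are not asked about in the intervention arm.**

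Understatement = (1 − POC uptake) × share of clients without a POC test who test elsewhere.

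Inputs: uptake of 90% (the expectation in 4.4) or about 97% (the community-testing figure cited there). The share is not in the documents. I assume 0 to 39%. The upper end borrows the plan's baseline rate, whose time window is not stated, and is probably high for people who did not take a free test on site.

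| POC uptake | Clients without POC test (of 250) | Understatement | Clients uncounted |
|---|---|---|---|
| 90% | 25 | 0 to 0.10 × 0.39 = 3.9 points | 0 to 9.75 |
| 97% | 7.5 | 0 to 0.03 × 0.39 = 1.17 points | 0 to 2.9 |

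For scale, missing 5% of intervention testers takes 74% to 0.74 × 0.95 = 70.3%, a drop of 3.7 points. Power is then about 84%.

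**3. Why the net direction is open.** Step 2 pulls toward no effect. Control outcomes, however, rest on follow-up and self-report, and errors there can go either way. The error rates below are assumptions. The odds ratios are simple marginal ones against 74%, with 4.45 as the error-free value.

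| Control-arm error | Observed control rate | Odds ratio |
|---|---|---|
| 10 / 20 / 30% of testers missed | 35.1 / 31.2 / 27.3% | 5.26 / 6.28 / 7.58 |
| 5 / 10 / 20% of non-testers report a test | 42.05 / 45.1 / 51.2% | 3.92 / 3.46 / 2.71 |

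**4. Clients of unknown status.** The plan gives no loss rate and no rule for classifying these clients. Assume 5 to 20% loss after tracing and 39% tested among control clients reached.

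- 5% loss: the control rate lies between 0.39 × 0.95 = 37.05% (all lost clients untested) and 37.05 + 5 = 42.05% (all tested).
- 20% loss: between 0.39 × 0.80 = 31.2% and 31.2 + 20 = 51.2%.

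**The case against.** The strongest reply is that the endpoint wording, not a clause about the purpose of a phone call, decides what counts. The endpoint is HIV testing, in both arms, without a POC limit. Sections 5.1 and 5.2 give purposes and are not a questionnaire, and 5.1 does not say that other tests are ignored. This stands. A reader might infer that the arms have two different outcome definitions, but the documents do not support that. What they show is one definition with unequal described data collection.

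Second, a reader might infer that no source covers both arms. That is also too strong. The exit survey goes to everyone, willingness to complete it is an entry criterion, and clinic-record access is consented to by all. On tracing, 5.3 says "This process will be followed for participants in both the intervention and control groups". What is missing is the assignment of a source to the endpoint. Equal tracing does not by itself make the questions equal.

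Third, part of 3.1 cannot be read: the Figure cited with the primary outcome is not shown, and the text before the sentence on selecting half the healers is missing. A source named only there cannot be excluded.

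Fourth, if 4.1 were applied strictly, almost every intervention client would take the POC test and the gap would shrink toward zero. But the optional wording in 5.1, the not-testing picture in the log and the 90% in 4.4 all anticipate some clients without a test. The 6.3 phrase on choosing not to test is weaker support, since it addresses both arms.

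**Conclusion.** The concern holds in a limited form. As worded, the monthly contacts would collect tests done elsewhere in control but not necessarily in the intervention arm, and the available text names no common source for the primary rate. On that mechanism alone the intervention rate is understated by 0 to 3.9 points at 90% uptake and 0 to 1.2 at 97%. This rests on the assumed 0 to 39% share, and on neither the exit survey nor clinic records being used to fill the gap. It is small beside 35 points. It merits correction because the remedy is cheap and the rates feed the next trial.

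Three stronger readings should be resisted:

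- **A net bias toward no effect.** That describes one mechanism. Missed control tests would inflate the effect, and the documents do not say which dominates.
- **An understatement of about 10 points**, from (1 − 0.74) × 0.39 = 10.1. This needs the 74% to be POC uptake alone, which the text does not say.
- **A fixed ratio of unknown outcomes between arms.** POC tests are known at the visit, so remaining loss may weigh more on control. But any ratio depends on the uptake chosen and on the intervention log being an endpoint source, which the plan does not state.

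**What to change.** - **Definition (Protocol Summary and 6.1):** state the primary outcome in both arms as any HIV test, healer POC or elsewhere, within 3 months of enrollment.
- **Data collection (5.1, 5.2, 6.3):** ask the 5.2 question about testing since enrollment, in identical form, in both arms at every monthly contact and in the exit survey. Name these as the endpoint source, with the intervention log as a supplement for POC tests.
- **Analysis (6.2):** add a sensitivity analysis that varies the outcome only for clients of unknown testing status, separately by arm, from all untested to all tested.

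Section 6.1 describes linkage for a positive HIV test, while the summary says a positive POC test. Narrowing 6.1 to POC is not part of this fix. Control healers give no POC tests, so control-arm positives would drop out of the linkage outcome and a new difference between arms would arise.

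The cost is a few added questions at contacts already planned and some protocol wording, with no new visits. Two weaknesses remain: tests done elsewhere still rest on self-report, and the sensitivity analysis shows the effect of lost clients without removing it.
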